10.4.2 Disease Activity Assessment

The Short Crohn's Activity Index (SCAI), the Simplified Pouchitis Disease Activity Index (PDAI), or the Simple Clinical Colitis Activity Index (SCCAI) questionnaire will be used to assess CD, Pouchitis, or UC disease activity, respectively (**Appendices 1 and 2**). These assessments include questions about patient overall well-being as well as specific symptoms and complications of CD or UC, such as stool frequency and abdominal pain.

Subjects will be questioned at each visit, V1, V2, and V3, regarding their clinical symptoms and subsequently scored accordingly.

Transplant Rejection

Episodes of acute rejection will be collected by searching electronic medical records and asking patients at each clinic visit V1, V2, and V3. Acute rejection will be defined as a notation of a new episode of acute rejection (cellular or antibody-mediated), a steroid bolus and taper in the absence of another indication, or administration of a T or B cell depleting agent or immune globulin.

10.4.3 Adverse Events Assessments

Adverse events data collection for this study begins at the time the subject signs the informed consent. Adverse event assessments included questioning subjects both at the follow-up phone call and at the follow-up visit regarding Adverse Events and SAEs.

Participants who do not fill out their vaccine diary or unable to be contacted at FU1 will be considered to have missing post immunization data. This data will be considered non-reported data.

10.4.4 Other Measurements

Medical history, including medications used to treat IBD or solid organ transplant, will be obtained from the subjects' medical records and entered into the research records. Medical history included all diagnoses and other diseases.

Medication history must be present in the subject's medical records and recorded in the subject's research records, including all prescription medications and nonprescription therapies taken within 30 days prior to the initial visit.

Data Handling and Record Keeping The only identifiers UNC will have access to are Subject ID numbers and dates of service and vaccination. They will not have access to linking coded data. The link to the subject ID will be maintained by UW research staff.

11.0 DATA HANDLING AND RECORD KEEPING

Data will be stored on a web-based platform to collect all patient-related information, disease activity, and other study questionnaires. This web-based platform will be developed by University of North Carolina. They will not be the data safety monitor for the study.

The University of North Carolina will serve as a Data Management Center (DMC) for this study. The work will be conducted in the Bioinformatics and Biostatistics Core of the Center for Gastrointestinal Biology and Disease (CGIBD). [name], will lead the DMC for this study. The Core has served as the Data Management Center for the Crohn's and Colitis Foundation Clinical Alliance. In that capacity the DMC has conducted a number of randomized trials and observational studies of IBD. They have also served as the Data Management Center for the Sinai Helmsley Alliance for Research Excellence which is a multicenter study of patients with IBD. The DMC will be charged with creating, managing, and housing the data management system.

The DMC will be responsible for all of the data management needs of the study. These activities will include, but not be limited to the following. They will build applications to collect baseline and follow-up data as specified in the protocol, generate reports about recruitment, enrollment, compliance, and dropouts, provide barcodes for biological specimens and build tracking programs for the specimens, provide data sets for analysis, and participate in data analysis and reporting. The only identifiers UNC will have access to are Subject ID numbers and dates of service. They will not have access to linking coded data. The link to the subject ID will be maintained by UW research staff.

Site Coordinators will collect data on source documents and will complete double data entry onto electronic CRFs in the data management system created by the DMC. Participants will collect data via direct data capture. All of the data will be maintained, archived, retrieved and distributed (except for the source documents completed by the Site Coordinators), by a computer system. The use of electronic records will increase the speed of data collection and exchange. Electronic records permit economical storage of study data and ease of accessibility and analysis. Data management and data quality systems will be built into the system. The DMC will have password-required access to the data management system where they can export data. UW will have password-required access to the data management system as well but they will only have access to their site's data and they will not be permitted to export the data.

The DMC at the CGIBD at the University of North Carolina will track the data collection, provide data security, control for confidentiality of study data, maintain computer backups to protect data until study closure and archive study data. Electronic signatures will be linked to each entry.

All computer systems and programs will be password protected, and all electronic communications of study and other confidential information will be encrypted. Personnel at the CGIBD have extensive training and experience using electronic data systems. Good computer security practice (restricting physical access to machines, prohibition of password sharing, and logging off computers after work hours or when away from the machine) will be required of all study personnel.

Standard Operating Procedures exist for users of the DMC. The DMC will be housed on an https secure website in order to protect the study participants' information. Only authorized persons are authorized for data entry and access. Data security systems require password protected identification codes for data entry and provide protection against data manipulation. The database is located on a server protected by firewalls. Access to the database server will not be allowed by

users on computers outside of the firewall-protected zone. Virus protection software is installed on each study machine. System access to computer systems will be audited. Redundant backups and off-site backup storage will allow for quick restoration of data in the unlikely event that a hardware failure, disaster, or security breach should occur. Servers and backups will be located in a secured location with access limited to authorized personnel.

Standardized study management reports will be generated monthly during the recruitment phase of the study. These reports will be used to track study progress including patient enrollment, randomization, compliance, patient status changes, and study events. The data will be reported for each Study Center individually and summarized for the study as a whole. Every six months, a standardized report will also be generated for meeting with University of Wisconsin team. This report will include additional information on clinical events and adverse events that is coded by treatment group. Other than the UW, the study statistician and statistical analyst, no study personnel will see this report.

Patient data from in-person visits will also be recorded in the electronic medical records. Any original subject files and protocol paperwork will be kept in the secured Office of Clinical Trials. We will keep these files within the Office of Clinical Trials until 2 years after the study completion at that time they will be archived to the State Record Center.

Transfer of data: LabCorp will perform quantitative COVID-19 antibody levels, they will transfer final data to UW for final analysis in files that will be password protect by LabCorp IT service.

Specimens at UW will be labeled with the subject's study ID number and date of collection so that the data collected for this protocol can be linked to the sample. Samples will be stored in Rennebohm Hall at the University of Wisconsin. Only investigators and key personnel assigned to the laboratory have access to the lab. Samples will be coded (labeled with subject ID and date of collection) before they arrive at the laboratory. All computers used for data storage and analysis are password protected and used exclusively by key personnel.

Any future studies that will use these specimens will be conducted by UW researchers and submitted for separate IRB approval. Only coded samples and data will be released for future research. Information linking the samples and data to individual participants will not be released.

All data will be labeled with the subject's study ID number and stored at the University of Wisconsin. Data will be stored in an Excel spreadsheet on secured servers and will only be accessible to those with a valid UW username and password with the right to see those files. The link connecting the subject ID number and study data will be stored separately from the study data. The servers are housed in locked cabinets inside locked, climate-controlled rooms. Access to UW servers is restricted by UW firewalls. Any connections to UW servers from outside the UW network must travel over UW Madison's virtual private network (VPN). This ensures that all communications between the UW and remote user are encrypted.

The samples shipped to LabCorp will be destroyed by them. Cell-mediated immunity will be analyzed, and the samples will be banked. Banked data may be used in future research to study the clinical outcomes of the COVID-19 vaccination and the sustained protection provided by the vaccine. These data may also be utilized to study the safety of vaccination and its long-term protection against COVID-19.

12.0 STUDY ANALYSIS

12.1 Number of Subjects (Statistical Justification)

We used results from our previous COVID-19 vaccine study to calculate our sample size needed for this study. We anticipate that antibody concentrations wane but with infection and multiple doses of vaccine, we estimated that the trough antibody concentration will be somewhat higher than it was after two doses of vaccine. The sample size 20 patients for this study was chosen based on feasibility and practicality of enrolling such patient populations. Therefore, a formal sample size estimation was not calculated, as the results would be deem descriptive and exploratory in nature. However, this sample size is sufficient to provide accuracy in estimating adverse event rates.

12.2. Statistical Analysis

In general, simple descriptive statistics will be provided to summarize demographics and baseline characteristics parameters. Categorical data will be summarized as frequency and its corresponding percentage. For continuous data, frequency (n), mean, standard deviation, median (as appropriate), minimum, and maximum will be provided for each of the parameters. A formal statistical analysis plan (SAP) will be developed before the database lock. It will include a detailed description of summaries and mock-ups of tables, listings, and figures to be included in the clinical study report.

In analyzing the primary endpoint, frequencies and percentages of antibody concentrations will be summarized in table formats. For exploratory purposes, a paired t-test will be utilized to test whether, on average, there is a change of at least 15% antibody blood concentration between the first and second blood draws. A test statistics and degrees of freedom, including the 95% confidence intervals will be reported

For the secondary endpoints, we will use descriptive statistics and formal tests (for exploratory purposes) to analyze the data, as described above, when appropriate and informative.

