- Evaluate for solid organ transplant rejection following administration of booster dose, up to 30 days post-vaccination and during the whole post-vaccination follow-up period

2024-2025 season

(The 2024-2025 season activities will not proceed as originally planned due to the withdrawal of financial support from our sponsor).

Primary Objective

• Humoral Immunogenicity of a *NVX-CoV2024-2025 booster*

Secondary Objectives

- Sustained antibody concentrations of the NVX-CoV2024-2025 booster.
- Seroconversion.
- Cell-mediated immunity to NVX-CoV2024-2025 booster
- Sustained cell-mediated immunity to the NVX-CoV2024-2025 booster
- Describe the safety of the NVX-CoV2024-2025 booster
- Evaluate the disease activity following administration of the booster dose up to 30 days post-last vaccination and during the whole post-vaccination follow-up period.
- Evaluate for solid organ transplant rejection following administration of booster dose, up to 30 days post-vaccination and during the whole post-vaccination follow-up period

2023-2024 Season

Primary Endpoint

Antibody concentrations at V2 are statistically significantly higher than at V1.

Secondary Endpoints

- Seropositivity rate at V2 and V3 in all participants.
- Individuals who achieve seroconversion at V2
- Interferon gamma responses at V2 compared to V1.
- Interferon gamma responses at V3 compared to V1.
- The number and percentage of subjects reporting solicited and unsolicited AEs, pIMDs, and SAEs.
- Number and percentage of participants reporting disease flares of IBD.
- Number and percentage of participants reporting acute rejection of their transplant.

2024-2025 Season

Primary Endpoint

Antibody concentrations at V2 are statistically significantly higher than at V1.

Secondary Endpoints

Endpoints

	 Seropositivity rate at V2 and V3 in all participants. Individuals who achieve seroconversion at V2 Interferon gamma responses at V2 compared to V1. Interferon gamma responses at V3 compared to V1. The number and percentage of subjects reporting solicited and unsolicited AEs, pIMDs, and SAEs. Number and percentage of participants reporting disease flares of IBD. Number and percentage of participants reporting acute rejection of their transplant.
Study Design	2023-2024 season This will be a single-center, prospective, unblinded, non-randomized study of 120 immunosuppressed patients who are planning to receive a NVX-CoV2601 COVID-19 vaccine booster dose. 2024-2025 season

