	This will be a single-center, prospective, unblinded, non-randomized study of 120 immunosuppressed patients who are planning to receive a NVX-CoV2024-2025 COVID-19 booster
FDA Regulatory Overview	The protocol uses an investigational product, NVX-CoV2601, and is being conducted under IND NUMBER 29913 that is held by [name].
Study Intervention	NVX-CoV26012023/2024 (monovalent, XBB containing) Novavax COVID-19 vaccine, the Omicron XBB.1.5 vaccine is named BV2601 NVX-CoV2024-2025 booster Novavax COVID-19 vaccine, the Omicron XBB.1.5 vaccine is named BV2601
Total Number of Subjects	2023-2024 season 21 patients were enrolled in this season 2024-2025 season (none will be recruited anymore) (The 2024-2025 season activities will not proceed as originally planned due to the withdrawal of financial support from our sponsor). A total 120 subjects will be enrolled.
Ota-la B	A total of 141 subjects will be enrolled for this study for both seasons.
Study Population	Male and females aged 18 to 85 with IBD and/or who are solid organ transplant recipients.
Statistical Methodology	In analyzing the primary endpoint, a paired t-test will be utilized to test whether, on average, there is a change of at least 15% antibody blood concentration between the first and second

	blood draws. A test statistics and degrees of freedom, including the 95% confidence intervals will be reported. In addition, we will model the post measurement blood draw concentrations (i.e., V2 and V3) as the response variable using an ANOVA (i.e., ANOVA-POST), while adjusting for the initial responses (V1) and other baseline covariates.
Estimated Subject Duration	The duration of the study for each subject is approximately 6 months.
Estimated Enrollment Period & Study Duration	Study enrollment and follow-up will occur over 6 months with the total expected duration of the trial to be 24 months.

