6.1 Primary Objective

The following objective will be evaluated separately based on the season 2023-2024 and 2024-2025.

Humoral Immunogenicity of a NVX-CoV2601/(2024/2025 COVID booster).

We will evaluate antibody concentrations 1 month after the recombinant vaccine booster (V2) in patients with IBD and solid organ transplant recipients compared to their baseline visit (V1). We measured antibody concentrations in patients with IBD one-month post-booster and found robust responses. We will measure anti-receptor binding domain (RBD) antibody levels and nucleocapsid antibodies in all participants at baseline and post-immunization.

Success Criterion: The objective of our primary endpoint will be achieved if the antibody concentration at V2 is at least 15% higher than at V1.

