7.4 Study Duration

Major Study Periods

First Patient In (FPI) to Last Patient In (LPI):

6 months
LPI to Last Patient Out (LPO):

6 months
LPO to manuscript

4 months

We will publish the first manuscript based on the vaccine response baseline compared to 1 month post immunization 4 months after LPI.

The second manuscript will be published after completion of the study.

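### The primary endpoint has two non-equivalent success statements, and its 15% paired t-test states no null or scale and is labelled exploratory in only one of two places

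*Combined protocol and SAP*

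**What the plan says.** Four places in the combined protocol and SAP bear on the primary endpoint.

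- **Section 3.0, Synopsis, primary endpoint:** "Antibody concentrations at V2 are statistically significantly higher than at V1".
- **Section 6.1, success criterion:** the objective "will be achieved if the antibody concentration at V2 is at least 15% higher than at V1". No test, confidence bound or summary measure is attached.
- **Section 3.0, Synopsis, statistical methodology:** here the plan reads "In analyzing the primary endpoint, a paired t-test will be utilized to test whether, on average, there is a change of at least 15" per cent. There is no exploratory label. The synopsis also lists a model of the post-vaccination values adjusted for V1, which section 12.2 does not mention.
- **Section 12.2:** the same test, introduced by "For exploratory purposes, a paired t-test will be utilized to test whether, on average, there is a change of at least 15" per cent. The test statistic, degrees of freedom and 95% CI are to be reported. Before that, "frequencies and percentages of antibody concentrations will be summarized in table formats".

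Section 12.1 adds that "a formal sample size estimation was not calculated, as the results would be deem descriptive and exploratory in nature". Every success criterion given for the secondary objectives in 6.2 to 6.5 is descriptive, so the primary objective is the only one with a pass/fail rule. Section 12.2 also promises a later document: "A formal statistical analysis plan (SAP) will be developed before the database lock".

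**The concern.** Significantly higher than baseline and at least 15% higher are different criteria. The first depends on the variability and on the number of pairs. The second, as written, depends only on an estimate, and the plan does not say which one (arithmetic means, geometric means or individual ratios).

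The t-test does not settle the matter. A test of a change of at least 15% could mean a test against no change with a 15% point estimate required as well, or a test against a ratio of 1.15. Its sentence gives no direction and no rule that turns the result into success.

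The status of the test also differs. It is exploratory in 12.2 and in keeping with 12.1, but it appears as the plain primary analysis in the synopsis.

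At stake is whether the trial reports its primary objective as achieved. In an unblinded single-arm study, an unsettled rule leaves room to choose after the results are known.

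**Working it through.** **No plan figure to reproduce.** Section 12.1 gives a feasibility-based size of 20 and no alpha, effect, SD or power. The calculation below only illustrates how far the two statements diverge.

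**Inputs**
- From the documents: 21 enrolled in 2023-2024 (synopsis). Section 10.3 defines enrolled as consented and vaccinated. The number with a V2 sample is not stated, so 21 pairs is an upper limit.
- Assumed: lognormal concentrations, log10 SD of V2/V1 s = 0.2 / 0.3 / 0.4, two-sided 5% tests, and true geometric mean rise g = 1, 1.5, 2 or 3.

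**Step 1. Standard error of the mean log10 ratio.** s/√21 = 0.0436 / 0.0655 / 0.0873.

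**Step 2. Observed rise each rule needs.**
- Section 6.1, read as a geometric mean: 1.15 at every SD.
- Synopsis endpoint on logs: 10^(t × SE) with t(0.975, 20) = 2.086, which gives 1.23 / 1.37 / 1.52 when the sample SD equals s.
- The two coincide where s = log10(1.15) × √21 / 2.086 = 0.0607 × 4.583 / 2.086 = 0.133. Above that SD the 6.1 rule is the looser one.

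**Step 3. No true rise (g = 1).** The chance that 6.1 is met is P(Z > 0.0607/SE), with 0.0607/SE = 1.39 / 0.93 / 0.70. This gives 8.2 / 17.7 / 24.3%. Significance in the upward direction occurs in 2.5%.

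**Step 4. True rise of 1.5-fold.**
- 6.1 met: P(Z > (0.0607 − 0.1761)/SE) = 99.6 / 96.1 / 90.7%.
- Significant against no change (noncentral t): 97.0 / 72.5 / 48.4%.
- In simulation (100,000 trials per scenario), significance without a 15% rise was essentially absent, so the share meeting 6.1 but not the synopsis is the difference: 2.6 / 23.6 / 42.3%.

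**Step 5. The same quantity across rises and numbers of pairs**

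| True rise | 21 pairs | 15 pairs |
|---|---|---|
| 1.5-fold | 3 / 24 / 42% | 10 / 37 / 51% |
| 2-fold | 0 / 1 / 9% | 0 / 5 / 22% |
| 3-fold | 0 / 0 / 0.1% | 0 / 0 / 1% |

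**Step 6. The unstated null.** Power on logs with 21 pairs at 1.5-fold is 97 / 72 / 48% against 1.0 and 71 / 39 / 24% against 1.15. At 2-fold it is 100 / 99 / 91% and 99.9 / 94 / 75%.

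**Step 7. The unstated scale, a separate matter.** Power for a doubling against no change is 100 / 99 / 91% on logs. On untransformed concentrations it is about 88 / 75 / 61% if the V1 log10 SD is 0.5 and the ratio is independent of V1, and 99 / 94 / 83% if the V1 log10 SD is 0.3. The order can reverse: at 1.5-fold with V1 SD 0.3 and ratio SD 0.4, the untransformed test passes in 60% and the log test in 48%.

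**The case against.** **The two statements are nearly nested.** Over the SDs used here, significance almost never occurs without a 15% rise, so requiring both amounts to requiring significance. A reader might infer two rival endpoints that can each pass where the other fails. The reverse case needs a log10 SD below about 0.13, outside the range shown. What stands is narrower: the 6.1 rule is the looser one and carries no error control.

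**The discordance at 2-fold and above is the t-test's type II error.** The 0 / 1 / 9% at 2-fold is essentially 100 minus the power of 100 / 99 / 91%. This is correct. It is not a separate harm added to low power, and at 3-fold it disappears on logs.

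**Direction is given.** The synopsis endpoint and 6.1 both say higher. The missing direction is confined to the test sentence.

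**The scale may be settled elsewhere.** A reader might infer that an untransformed analysis is planned. The documents are silent on scale. The general text of 12.2 also lists mean, SD, median and range for continuous data, although that sentence follows one on baseline parameters.

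**The promised SAP may resolve this.** A reader might infer that it will come after the primary results, because 7.4 says "We will publish the first manuscript based on the vaccine response baseline compared to 1 month post immunization 4 months after LPI" and puts last patient out at 6 months after last patient in. That is a planning timetable. The absence of a separate V1-V2 lock is inferred from silence, so late timing is not shown. A later SAP would, however, leave the protocol sections disagreeing.

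**The work is exploratory and recruitment is over.** This limits the consequence, and reporting the 95% CI lets readers judge for themselves. It does not explain why the synopsis and 6.1 keep a significance endpoint and a success rule.

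**Conclusion.** The concern holds as an inconsistency in the current text. There are two non-equivalent success statements, a t-test without a null or a scale, and an exploratory label in 12.2 that the synopsis lacks. These findings rest on the wording and need no assumption.

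The practical weakness is that the 6.1 rule can be met by chance. Under the stated assumptions this happens in about 8 / 18 / 24% of trials with no true rise. It diverges materially from the synopsis endpoint only for modest rises: 3 / 24 / 42% at 1.5-fold, 0 / 1 / 9% at 2-fold and about none at 3-fold. The documents give neither an expected rise nor an SD, so none of these can be called the likely case. The lower power of an untransformed test is a secondary observation that depends on the V1 SD and is not universal.

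Severity is the low end of should-fix, close to minor, because section 12 already treats the results as descriptive and exploratory.

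**What to change.** State one position in identical words in the synopsis, 6.1 and 12.2.

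- **Analysis:** use log(V2/V1) per participant. Report geometric mean concentrations at V1 and V2, the geometric mean fold rise with a two-sided 95% CI, and the number of pairs, in place of frequencies and percentages. State the value used for results below the assay limit.
- **Preferred, consistent with 12.1 and 12.2:** make the primary success criterion descriptive, as for the secondary objectives, and remove both the 15% and the significance wording.
- **If a rule is kept:** state its null (1.0 or 1.15), direction and alpha, and carry the same exploratory label in all three places. Dropping the label would give confirmatory status to a study of about 20 with no power calculation.
- **Timing:** make the change by dated amendment before the V1-V2 data are analysed. If they have already been seen, mark the change as post hoc and report the result under both existing statements.
- **Adjusted model:** delete the V1-adjusted model from the synopsis or add it to 12.2.

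The cost is wording in three places and no new data. The preferred option gives up a pass/fail claim. Keeping a rule with a null of 1.15 instead of 1.0 costs the power shown in step 6.
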